###### Cardiac Telemetry

The number and percentage of subjects with telemetry result of “normal,” “abnormal but clinically insignificant,” and “abnormal and clinically significant” will be summarized by

treatment group. The number and percentage of subjects with specific telemetry abnormalities will be summarized by treatment group.

## **Vital Signs**

### *Vital Signs*

Each vital sign parameter and the changes in value from baseline will be summarized by treatment group at every assessed time point using n, mean, standard deviation, median, minimum, and maximum.

## 8. PHARMACOKINETIC ANALYSES

### 8.1. Pharmacokinetic Analyses

#### 8.1.1. Endpoint / Variables

##### 8.1.1.1. Drug Concentration Measures

Refer to [Appendix 4](#): Data Display Standards & Handling Conventions (Section 9.4.3 Reporting Standards for Pharmacokinetic)

##### 8.1.1.2. Derived Pharmacokinetic Parameters

Pharmacokinetic parameters will be calculated by standard non-compartmental analysis according to current working practices and using the currently supported version of WinNonlin 6.3 or higher. All calculations of non-compartmental parameters will be based on actual sampling times. Pharmacokinetic parameters listed will be determined from the plasma concentration-time data, as data permits.

Parameter	Parameter Description
AUC(0-7), AUC(7-14), AUC(14-24), AUC(0-24)	
The area under the concentration-time curve will be calculated to some fixed nominal time x (AUC(0-x)), using the combination of linear and logarithmic trapezoidal methods (i.e., Linear Up/Log Down calculation method in Phoenix WinNonlin Professional).
 
If a sampling time deviation occurred at nominal time x (and x < t), AUC(0-x) will be calculated using the concentration at time x post-dose estimated by the method of interpolation. If nominal time x > t (or if the concentration at time x was below the limit of quantification), then the concentration (y) at time x is estimated using lambda_z and last observed Ct according to the formula:
 $y = Ct(\text{obser}) \times e^{-\lambda_z(x-t)}$ 
Then the following equation will be used to calculate (AUC(0-x)) where t is the time of last quantifiable plasma concentration.
 $\text{AUC}(0-x) = \text{AUC}(0-t) \times \text{AUC}(t-x)$ 
If lambda_z is not estimable, a partial AUC is not calculated (when x > t).

Cmax	Maximum observed plasma concentration following each dose will be obtained directly from the concentration-time data.
Tmax	The time to maximum observed plasma drug concentration following each dose will be obtained directly from the concentration-time data.
t1/2	Terminal half-life following the 3rd dose will be calculated as follows: $t_{1/2} = \ln 2 / \lambda_z$
C0	The plasma drug concentration at 0 hour will be obtained directly from the observed concentration-time data.
C7	The plasma drug concentration at 7 hours will be obtained directly from the observed concentration-time data.
C14	The plasma drug concentration at 14 hours will be obtained directly from the observed concentration-time data.
C24	The plasma drug concentration at 24 hours will be obtained directly from the observed concentration-time data.

Parameter	Parameter Description
lambda_z	The first order rate constant associated with the terminal (log-linear) portion of the curve following the 3rd dose.
lambda_z lower	The lower limit on time for values to be included in the calculation of lambda_z following the 3rd dose..
lambda_z upper	The upper limit on time for values to be included in the calculation of lambda_z following the 3rd dose..
#pts	The number of time points used in computing lambda_z following the 3rd dose..
R-square	Square of the correlation coefficient for computing lambda_z following the 3rd dose.

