### Model Specification

- Dose proportionality for AUC(0-24), AUC(0-7) and Cmax following the first (morning) dose will be assessed by using a power model as described below:

$$\log_e (Y_{ij}) = \mu + S_i + \beta * \log_e (D_j) + \varepsilon_{ij}$$

$Y_{ij}$ : PK parameter (AUC(0-24), AUC(0-7), Cmax) on dose j for subject i

$\mu$ : Overall mean (intercept)

$\beta$ : slope for  $\log_e$  transformed dose

$S_i$ : random effect for subject i following normal distribution  $N(0, \sigma_b^2)$

$D_j$ : dose effect ( $j = 60$  mg,  $120$  mg,  $240$  mg)

$\varepsilon_{ij}$ : random error following normal distribution  $N(0, \sigma_w^2)$

- The model parameters will be estimated using Restricted Maximum Likelihood with the Newton-Raphson algorithm.
- The Kenward-Roger degree of freedom approach will be used.

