#### 9.4.3. Reporting Standards for Pharmacokinetic

Pharmacokinetic Concentration Data	
PC Windows Non-Linear (WNL) File	PC WNL file (CSV format) for the non compartmental analysis by Clinical Pharmacology Office function will be created according to GUI_51487. Note: Concentration values will be imputed as per GUI_51487
Descriptive Summary Statistics, Graphical Displays and Listings	Refer to IDSL PK Display Standards. Refer to IDSL Statistical Principle 6.06.1. Note: Concentration values will be imputed as per GUI_51487 for descriptive summary statistics/analysis and summarized graphical displays only.
Pharmacokinetic Parameter Derivation	
PK Parameter to be Derived by Programmer	The following PK parameters will be derived by the Programmer: [C0, C7, C14, C24]
Pharmacokinetic Parameter Data	
Is NQ impacted PK Parameters Rule Being Followed	Yes, refer to GUI_51487.
Descriptive Summary Statistics, Graphical Displays and Listings	Refer to IDSL PK Display Standards. Refer to [Insert document name]

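### As extracted, the SAP's equation for an extrapolated AUC multiplies two adjacent areas where it should add them (confirm the operator on the source page)

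*SAP*

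**What the plan says.** The AUC row of the parameter table in SAP 8.1.1.2 names the calculation rule as "Linear Up/Log Down calculation method in Phoenix WinNonlin Professional". It then covers a nominal end time x that lies after the last quantifiable time t, or a sample at x that is below quantification. There, "the concentration (y) at time x is estimated using lambda_z and last observed Ct according to the formula" y = Ct × exp(−lambda_z(x − t)). The row continues: "Then the following equation will be used to calculate (AUC(0-x)) where t is the time of last quantifiable plasma concentration". The equation that follows, in the extracted markup, is "AUC}(0-x) = \text{AUC}(0-t) \times \text{AUC}(t-x", a product of AUC(0-t) and AUC(t-x). One restriction closes the row: "If lambda_z is not estimable, a partial AUC is not calculated" when x is after t.

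Protocol 10.4.2 lists the AUC parameters and names WinNonlin but gives no extrapolation equation. Neither document states the additive form anywhere.

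**The concern.** The equation is worded as the rule to be used, not as an illustration, and it cannot be right as it stands. AUC(0-24) and AUC(14-24) are PK endpoints (SAP 2.2). AUC(0-24) is also a response in the power model, which the SAP specifies as "Dose proportionality for AUC(0-24), AUC(0-7) and Cmax following the first (morning) dose". Anyone who applied the rule literally, or used it to check the software's output, would get a wrong AUC for every extrapolated profile.

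The rule can be reached. A subject may leave or miss samples between the third dose and 24 h, and SAP 9.6.1 keeps the available planned data of withdrawn subjects in the summaries.

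**Working it through.** The plan states no number here to reproduce, so the check is on the formula itself.

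**Inputs**
- The product equation, the formula for y and the log-down rule: SAP 8.1.1.2.
- Predicted mean AUC(0-24) at 240 mg TID, 40.2 µg·h/mL, used only for scale: Protocol 5.7.
- Half-life of about 2 to 6 h: Protocol 3.2 (Protocol 5.6 gives 2 to 3 h).
- Dosing at 0, 7 and 14 h: Protocol 5.1.
- Assumed for illustration only: one-compartment oral profile, absorption rate 1.5/h, last quantifiable time t of 19 or 22 h.

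**1. Definition.** An area under a curve is an integral, so for t < x, AUC(0-x) = AUC(0-t) + AUC(t-x).

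**2. The segment the SAP sets up.** Under the log-down rule, with y from the SAP's own formula, AUC(t-x) = (Ct − y)/lambda_z. The purpose of estimating y is to close this segment, which is then added to AUC(0-t).

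**3. Limit.** As x approaches t, y approaches Ct and the segment goes to 0. The sum tends to AUC(0-t), as it must. The product tends to 0.

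**4. Units.** The left side is in µg·h/mL and the product in (µg·h/mL)². An assumed split of the 40.2 prediction shows the consequence:
- In µg·h/mL: sum 40.0 + 0.2 = 40.2; product 40.0 × 0.2 = 8.0; ratio 8.0/40.2 = 0.20.
- In ng·h/mL: sum 40,000 + 200 = 40,200; product 40,000 × 200 = 8,000,000; ratio 8,000,000/40,200 = 199.

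The two ratios differ by the unit factor of 1000. A valid formula gives the same area in either unit.

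**5. Simulated profiles.** Each profile is scaled so that the true AUC(0-24) is 40.2 µg·h/mL, with x = 24 h.

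| Half-life (h) | t (h) | AUC(0-t) | AUC(t-24) | Sum | Product | Product / sum |
|---|---|---|---|---|---|---|
| 2 | 19 | 37.38 | 2.81 | 40.19 | 105.2 | 2.62 |
| 2 | 22 | 39.59 | 0.61 | 40.20 | 24.0 | 0.60 |
| 3 | 19 | 35.76 | 4.44 | 40.20 | 158.7 | 3.95 |
| 3 | 22 | 39.00 | 1.20 | 40.20 | 46.8 | 1.16 |
| 6 | 19 | 32.97 | 7.22 | 40.20 | 238.2 | 5.93 |
| 6 | 22 | 37.80 | 2.40 | 40.20 | 90.8 | 2.26 |

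Addition recovers the true area to within 0.01 in every row. The product ranges from 24.0 to 238.2.

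**6. How often the rule would apply.** PK samples after 24 h are scheduled at 28, 32, 36, 48, 60 and 72 h, six in all (Protocol section 2; SAP 9.2.1). For a subject with complete sampling, t should therefore normally lie beyond 24 h. Lambda_z is defined only after the third dose, so the rule bears mainly on AUC(0-24) and AUC(14-24).

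**The case against.** The strongest objection is that this may not be the sponsor's error. The operator was read from the PDF by a program, and a legitimate multiplication sign stands in the formula for y just above it. Other symbols in the text are doubtful: Protocol 3.1 reads T1D where the synopsis has TID, and a time formula in SAP 9.3.1.1 lacks an operator before its final 1. This stands as a reason to look at the page. It does not show a misread, since the plus signs in the model equations of SAP 8.1.5.1 came through correctly.

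Second, the intended calculation is clear and nobody is assigned to code this line. SAP 9.4.3 says "PC WNL file (CSV format) for the non compartmental analysis by Clinical Pharmacology Office function will be created according to GUI_51487", and separately "The following PK parameters will be derived by the Programmer: [C0, C7, C14, C24"; the AUCs are not on that list. This is correct and is the main reason the point is minor.

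Third, the rule should rarely be needed. At 24 h the third dose is 10 h old. With the shortest stated half-life of 2 h that is 10/2 = 5 half-lives, leaving about 1/2⁵ = 1/32. Protocol 3.2 reports PK from single doses as low as 0.1 mg, and 60/0.1 = 600. If assay sensitivity is similar (no quantification limit is given), concentrations at 24 h should usually be measurable. This also stands, although missed samples remain possible.

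Finally, the ratios in the working do not forecast any effect in this trial. That is right: for areas a and b the ratio is ab/(a + b), which depends on the assumed split and the unit. They show only that the formula is invalid.

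**Conclusion.** The point holds for the text as extracted. The rule is wrong by definition, by units and in the limit, and none of these arguments needs assumed data. It contradicts the trapezoidal method in the same cell, and nothing elsewhere corrects it.

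It is a minor specification error with a small expected effect on reported AUCs; no bias in the PK results or in the dose-proportionality conclusion is predicted. Confidence is medium, because everything rests on one machine-read operator.

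**What to change.** Look at the equation on the source page of SAP 8.1.1.2. If the operator is a multiplication sign, change the line to AUC(0-x) = AUC(0-t) + AUC(t-x). If the page already shows a plus sign, withdraw the point. The cost is the page check and one character in the SAP; no dose, schedule, data collection or analysis model is affected.

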**NOTES:**

- Additional parameters may be included as required.
- Lambda\_z is the terminal phase rate constant.
- Ct is the last observed quantifiable concentration.

**8.1.2. Summary Measure**

The slope of log-transformed dose in the power model for AUC(0-24), AUC(0-7) and Cmax will be used as measure of the dose proportionality between dose and the PK parameters..

**8.1.3. Population of Interest**

The primary pharmacokinetic analyses will be based on the Pharmacokinetic population, unless otherwise specified.

**8.1.4. Strategy for Intercurrent (Post-Randomization) Events**

Intercurrent events which may affect the assessment of the safety and tolerability and the characterization of PK profile will not be anticipated.

**8.1.5. Statistical Analyses / Methods**

Details of the planned displays are provided in [Appendix 9: List of Data Displays](#) and will be based on GSK Data Standards and statistical principles.

Unless otherwise specified, endpoints / variables defined in Section [8.1.1](#) will be summarised using descriptive statistics, graphically presented (where appropriate) and listed.

**8.1.5.1. Statistical Methodology Specification**

The following pharmacokinetic statistical analyses will only be performed if sufficient data is available (i.e. if participants have well defined plasma profiles).

Endpoint / Variables

 
• Derived PK parameters for GSK2982772 (AUC(0-24), AUC(0-7), Cmax)
 

### Model Specification

- Dose proportionality for AUC(0-24), AUC(0-7) and Cmax following the first (morning) dose will be assessed by using a power model as described below:

$$\log_e (Y_{ij}) = \mu + S_i + \beta * \log_e (D_j) + \varepsilon_{ij}$$

$Y_{ij}$ : PK parameter (AUC(0-24), AUC(0-7), Cmax) on dose j for subject i

$\mu$ : Overall mean (intercept)

$\beta$ : slope for  $\log_e$  transformed dose

$S_i$ : random effect for subject i following normal distribution  $N(0, \sigma_b^2)$

$D_j$ : dose effect ( $j = 60$  mg,  $120$  mg,  $240$  mg)

$\varepsilon_{ij}$ : random error following normal distribution  $N(0, \sigma_w^2)$

- The model parameters will be estimated using Restricted Maximum Likelihood with the Newton-Raphson algorithm.
- The Kenward-Roger degree of freedom approach will be used.

### Model Checking & Diagnostics

- If the power model has failed to converge, dose proportionality will be assessed using ANOVA.
  - Assessment of dose proportionality using ANOVA

- The dose-normalized PK parameters (AUC(0-24), AUC(0-7), Cmax) will be calculated by dividing the PK parameters by dose.

- The dose-normalized values will be analyzed by using the following model.

$$\log (X_{ij}) = \mu + S_i + D_j + \varepsilon_{ij}$$

$X_{ij}$ : dose-normalized PK parameter (AUC(0-24), AUC(0-7), Cmax) on the dose j for subject i

$\mu$  : Overall mean

$S_i$ : random effect for subject i following normal distribution  $N(0, \sigma_b^2)$

$D_j$ : dose effect ( $j = 60$  mg,  $120$  mg,  $240$  mg)

$\varepsilon_{ij}$ : random error following normal distribution  $N(0, \sigma_w^2)$

the model has dose as fixed effect and subject as random effect.

- Point estimates and associated 90% confidence intervals for the differences  $60$  mg –  $120$  mg,  $240$  mg –  $120$  mg will be constructed using the residual variance. These confidence intervals will then be exponentially back-transformed to provide point estimates and associated 90% confidence intervals for the ratio  $60$  mg/ $120$  mg and  $240$  mg/ $120$  mg.

### Model Results Presentation

- The point estimates of the slope for each parameter and their 90% confidence intervals will be presented.

### 8.1.6. Details of Planned Pharmacokinetic Displays

#### Plasma Concentration-Time Data

The plasma concentrations at every scheduled time point will be summarized using n, mean, standard deviation, median, minimum, and maximum.

#### Derived Plasma Pharmacokinetic Parameters (non-transformed)

The plasma pharmacokinetic parameters (AUC(0-7), AUC(7-14), AUC(14-24), AUC(0-24), Cmax, Tmax, t1/2, C0, C7, C14, C24) will be summarized using n, mean, 95% CI, standard deviation, median, minimum, and maximum.

#### Derived Plasma Pharmacokinetic Parameters (log-transformed)

For each pharmacokinetic parameters with a log-normal distribution (AUC(0-7), AUC(7-14), AUC(14-24), AUC(0-24), Cmax, t1/2, C0, C7, C14, C24), the log-transformed parameters will be summarized using n, geometric mean, 95% CI of geometric mean, standard deviation of log-transformed data and between subject coefficient of variation (%CVb).

#### Power Model Analysis for Dose Proportionality of Pharmacokinetic Parameters AUC(0-24), AUC(0-7) and Cmax

The analysis results will be presented as described in Section 8.1.5.1.

## **9. APPENDICES**

### **9.1. Appendix 1: Protocol Deviation Management and Definitions for Per Protocol Population**

Protocol deviations will be tracked by the study team throughout the conduct of the study in accordance with the PDMP and the data handling will be determined prior to DBR.

CONFIDENTIAL

205037

## 9.2. Appendix 2: Schedule of Activities

### 9.2.1. Protocol Defined Schedule of Events

#### Time and Events Table for Screening and Follow-up Assessments

Procedure	Screening 	Follow-up Visit 	Notes
Outpatient Visit	X	X	
Informed Consent	X		
Medical/medication/drug /alcohol history	X		
Demographics	X		
Physical Examination	X	X	Additional examinations may be performed, by the Investigators, as deemed necessary (e.g., where safety or laboratory findings indicate).
Drug screen	X		Additional tests may be performed by the Investigators, as deemed necessary (e.g., where safety or laboratory findings indicate). Tests will be conducted within site specified standards.
Syphilis, Human immunodeficiency virus (HIV), Human T-cell leukemia virus type 1 (HTLV-1), Hepatitis B (Hep B) and Hepatitis C (Hep C) screen	X		
Tuberculosis (TB) Test	X		Conducted at the standard practice of the site.
X-ray Test	X		Anterior & lateral chest X-ray will be taken.
Hema/Chem/Urinalysis tests	X	X	
Height and weight	X		
12-lead ECG and vital signs	X	X	Vital signs to include pulse rate (PR), blood pressure (BPs) and temperature.
AE Review	X	X	All Serious Adverse Effects (SAEs) will be collected from the signing of the informed consent form (ICF) until the follow-up visit at the time points specified. All AEs will be collected from the start of treatment until the follow-up visit at the time points specified.
Concomitant Medication Review	X	X	

1: Within 30 days prior to the first dosing

2: Follow-up Visit to occur at least 7 days, and no greater than 14 days after last study treatment administration. If a participant withdrew from the study after received GSK2982772 or placebo dose, the safety assessments listed at follow-up visit will be required.

CONFIDENTIAL

205037

**Detailed Time and Events Table for Days 1-4 (common Period1-4)**

Procedure 	Da y -1	Day 1																				
		Pre-dose	0	20 min	40 min	1 hr	1.5 hr	2 hr	3 hr	4 hr	5 hr	7 hr	7 hr 20 min	7 hr 40 min	8 hr	8.5 hr	9 hr	10 hr	12 hr	14 hr	14 hr 20 min	14 hr 40 min
Admission	X																					
Physical Examination	X	X																				
Hema/Chem/Urinalysis tests	X																					
Vital signs 		X						X											X	X		
12-lead ECG		X						X											X 	X		
Cardiac telemetry		<=====																				
PK blood sampling		X		X	X	X	X	X	X		X	X	X	X	X	X	X	X	X	X	X	
Neurological Examination	X							X												X		
Study Treatment			X									X								X		
Pharmacogenetic Sample (PGx) 		<=====																				
Meals Served	X									X 									X 			
AE Review 		<=====																				
Concomitant Medication Review		<=====																				
Discharge																						

## CONFIDENTIAL

205037

Procedure 	Day 2								Day 3		Day 4
	16 hr	17 hr	19 hr	22 hr	24 hr	28 hr	32 hr	36 hr	48 hr	60 hr	72 hr
Admission											
Physical Examination					X			X	X		X
Hema/Chem/ Urinalysis tests											X
Vital signs 					X				X		X
12-lead ECG					X				X		X
Cardiac telemetry	=====>										
PK blood sampling	X	X	X	X	X	X	X	X	X	X	X
Neurological Examination					X				X		X
Study Treatment											
Pharmacogenetic Sample (PGx) 	=====>										
Meals Served					X 	X 	X 		X 	X 	
AE Review 	=====>										
Concomitant Medication Review	=====>										
Discharge											X

1: In this study, baseline is Day -1 and Day 1 pre-dose tests.

2: Vital signs include PR, BPs and temperature. A 14 hr time point is to be performed prior to third dose.

3: A PGx blood sample will be collected at any time during the study after randomization. The participation is optional for each subject.

4: All SAEs will be collected from the signing of the ICF until the follow-up visit at the time points specified. All AEs will be collected from the start of treatment until the follow-up visit at the time points specified.

5: Physical Examination and 12-lead ECG of 14hr time point are to be performed prior to third dose.

6: On Day 1, lunch will be served between 2 to 3 hr prior second dose.

7: On Day1, dinner will be served between 2 to 3 hr prior to third dose.

8: On Day 2-3, meal will be served per unit schedule. Mealtimes will be described in SRM.

### 9.3. Appendix 3: Study Phases and Treatment Emergent Adverse Events

#### 9.3.1. Study Phases

Assessments and events will be classified according to the time of occurrence relative to the date of dosing date.

Study Phase	Definition
Pre-Treatment	Date $\leq$ Previous Day of Dosing Date in Period 1
Period 1	Previous Day of Dosing Date in Period 1 $\leq$ Date $<$ Previous Day of Dosing Date in Period 2
Period 2	Previous Day of Dosing Date in Period 2 $\leq$ Date $<$ Previous Day of Dosing Date in Period 3
Period 3	Previous Day of Dosing Date in Period 3 $\leq$ Date $<$ Previous Day of Dosing Date in Period 4
Period 4	Previous Day of Dosing Date in Period 4 $\leq$ Date

#### 9.3.1.1. Study Phases for Adverse Events

Study Phase	Definition
Pre-Treatment	AE Onset Date and Time $<$ Study First Dosing Date and Time
Period 1	Dosing Date and Time in Period 1 $\leq$ AE Onset Date and Time $<$ Dosing Date and Time in Period 2
Period 2	Dosing Date and Time in Period 2 $\leq$ AE Onset Date and Time $<$ Dosing Date and Time in Period 3
Period 3	Dosing Date and Time in Period 3 $\leq$ AE Onset Date and Time $<$ Dosing Date and Time in Period 4
Period 4	Dosing Date and Time in Period 4 $\leq$ AE Onset Date and Time
Time since Study First Dose (min)	If study phase of the event is pre-treatment, AE Onset Date and Time - Study First Dosing Date and Time 1 otherwise AE Onset Date and Time – Study First Dosing Date and Time + 1 min
Time since Period First Dose (min)	If study phase of the AE is pre-treatment, set to missing If study phase of the AE is period 1, AE Onset Date and Time – Dosing Date and Time in Period 1 + 1 min If study phase of the AE is period 2, AE Onset Date and Time – Dosing Date and Time in Period 2 + 1 min If study phase of the AE is period 3, AE Onset Date and Time – Dosing Date and Time in Period 3 + 1 min If study phase of the AE is period 4, AE Onset Date and Time – Dosing Date and Time in Period 4 + 1 min
Time since Last Dose (min)	If study phase of the AE is pre-treatment, set to missing If study phase of the AE $\geq$ Study Last Dosing Start Date and Time, AE Onset Date and Time – Study Last Dosing Start Date and Time+ 1 min
Duration (min)	AE Resolution Date and Time – AE Onset Date and Time + 1 min
Drug-related	If relationship is marked 'YES' on eCRF or value is missing.

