5. STUDY DESIGN

5.1. Overall Design

This study will be a double-blind with respect to subjects, investigators and site staff (with the exception of the unblinded site pharmacist), TID oral doses for one day,

ascending dose, randomized, placebo-controlled, 4-way crossover study, shown as the table below;

Group	N	Period 1	Period 2	Period 3	Period 4
A	3	Placebo, TID	60 mg, TID	120 mg, TID	240 mg, TID
B	3	60 mg, TID	Placebo, TID	120 mg, TID	240 mg, TID
C	3	60 mg, TID	120 mg, TID	Placebo, TID	240 mg, TID
D	3	60 mg, TID	120 mg, TID	240 mg, TID	Placebo, TID

Treatment Groups and Duration:

Screening	Within 30 days prior to the first dose on Day1.
Treatment Period	
The study will be comprised of four study periods each at least 7 days in duration with subjects in-house for 4 nights (through 72 hrs after the first dose). During each treatment period, subjects will be admitted to the unit the day before dosing and will be discharged after completion of the 72 hrs post-dose assessments.
 
Each subject will receive oral TID doses of GSK2982772 in each treatment period. For TID dosing, GSK2982772 or placebo will be administered at 0 hr (the first dosing), 7 hr (the second dosing) and 14 hr (the third dosing) on Day 1 in each period. On Day 1, subjects will fast 8hr overnight prior to first dose. A breakfast will be served approximately 2hr after first dose. Lunch and dinner will be served between 2 to 3hr prior to second and third doses, respectively.

Washout Period	Will be at least 7 days between treatment period doses for an individual subject.
Follow-up	At least 7 days, and no greater than 14 days after last study treatment administration. If warranted, additional follow-up visits may be scheduled.

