9.1.1. Time Period and Frequency for Collecting AE and SAE Information

- All SAEs will be collected from the signing of the ICF until the follow-up visit at the time points specified in the SoA (Section 2).
- All AEs will be collected from the start of treatment until the follow-up visit at the time points specified in the SoA (Section 2).
- Medical occurrences that begin before the start of study treatment but after obtaining informed consent will be recorded on the Medical History/Current Medical Conditions section of the CRF not the AE section.
- All SAEs will be recorded and reported to the GSK or designee immediately and under no circumstance should this exceed 24 hrs, as indicated in Appendix 4. The

investigators will submit any updated SAE data to the GSK within 24 hrs of it being available.

- Investigators are not obligated to actively seek AEs or SAEs in former study participants. However, if the investigators learns of any SAE, including a death, at any time after a participant has been discharged from the study, and he/she considers the event to be reasonably related to the study treatment or study participation, the investigators must promptly notify the GSK.
- The method of recording, evaluating, and assessing causality of AEs and SAEs and the procedures for completing and transmitting SAE reports are provided in Appendix 4.

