#### 7.1.1. Details of Planned Adverse Events Summaries

##### Adverse Events (AEs)

###### All AEs by SOC and PT

The number and percentage of subjects with all relevant adverse events will be summarized by MedDRA System Organ Class and Preferred Term by treatment group. The counting of events and the percentages will be based on the number of subjects on each treatment, so subjects may appear in more than one treatment category.

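### The adverse event (AE) windows behind Tables 2.1-2.2 can differ in length by dose, so background events alone can modestly raise or lower the 240 mg percentages

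*SAP*

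**What the plan says.** SAP 9.3.1.1 defines the AE study phases. The Period 1, 2 and 3 windows each start at that period's dosing and end just before the next period's dosing. The Period 4 window starts at "Dosing Date and Time in Period 4" and the SAP gives it no end. The same section uses the period dosing time to derive *Time since Period First Dose*, so the clock starts at the first of the three daily doses.

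The protocol fixes the lengths only loosely. On the washout, Protocol 5.1 says: "Will be at least 7 days between treatment period doses for an individual subject". On follow-up it says: "At least 7 days, and no greater than 14 days after last study treatment administration". Protocol 9.1.1 closes AE collection: "All AEs will be collected from the start of treatment until the follow-up visit".

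SAP 7.1.1 describes the by-treatment AE tables: "The counting of events and the percentages will be based on the number of subjects on each treatment". No person-time denominator, fixed risk window or sensitivity table is listed. Protocol 10.4.1 plans no formal comparison; placebo is compared by reading the descriptive summaries.

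**The concern.** Every treatment is given to 12 subjects, so the denominators match. The time over which an event can be counted need not match, because treatment is tied to period by the ascending design. Only Period 4 is closed by follow-up rather than by another dosing, and three quarters of the 240 mg exposures are in Period 4.

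Protocol 5.6 gives the purpose of the placebo: to separate treatment-related AEs from those that would have occurred anyway. Window length acts on exactly the second kind. In a table of 12 per treatment that is read by eye, one or two extra or missing subjects at the top dose can look like a dose trend, or conceal one. AEs are the first-listed safety endpoint.

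**Working it through.** **The plan's own precision figure.** Protocol 10.1 states exact 95% upper limits of 26.5% for 0/12 and 38.5% for 1/12. The first is 1 - 0.025^(1/12) = 26.46%; the Clopper-Pearson limit for 1/12 is 38.48%. Both reproduce. The documents give no time at risk per treatment, so that has to be built from the sequences.

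**Exposures by period** (Protocol 7.2 sequences, 3 subjects each, 12 completers assumed):

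| Treatment | P1 | P2 | P3 | P4 |
|---|---|---|---|---|
| Placebo | 3 | 3 | 3 | 3 |
| 60 mg | 9 | 3 | 0 | 0 |
| 120 mg | 0 | 6 | 6 | 0 |
| 240 mg | 0 | 0 | 3 | 9 |

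**Mean window.** Let W be the days from one period's first dose to the next period's first dose, and F the days from the Period 4 first dose to follow-up. Follow-up is timed from the last administration, 14 h (0.58 day) after the first, so F runs from 7.58 to 14.58.

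- 60 and 120 mg: W
- Placebo: (9W + 3F)/12
- 240 mg: (3W + 9F)/12
- 240 mg minus 60 or 120 mg: 0.75(F - W)
- 240 mg minus placebo: 0.5(F - W)

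| W | F | Placebo | 60 and 120 mg | 240 mg | Ratio 240:60 mg |
|---|---|---|---|---|---|
| 7 | 7.58 | 7.15 | 7 | 7.44 | 1.06 |
| 7 | 14.58 | 8.90 | 7 | 12.69 | 1.81 |
| 14 | 14 | 14 | 14 | 14 | 1.00 |
| 14 | 7.58 | 12.40 | 14 | 9.19 | 0.66 |

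The documents set no upper limit on W; 14 days is an assumption. If the 7-day washout is counted from the third dose, W is at least 7.58, and the largest ratio is 12.83/7.58 = 1.69.

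**Effect on the percentages.** The documents give no background AE rate. Assume a constant first-event hazard h, equal on all treatments (no drug effect), at 0.01, 0.02 and 0.05 per day. The expected proportion with an event in a window of t days is 1 - exp(-ht). The expected difference in subjects is then:

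- 240 mg against 60 or 120 mg: 9[exp(-hW) - exp(-hF)]
- 240 mg against placebo: 6[exp(-hW) - exp(-hF)]

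| W, F | h | Against placebo | Against 60 or 120 mg |
|---|---|---|---|
| 7, 14.58 | 0.01 | +0.41 | +0.61 |
| 7, 14.58 | 0.02 | +0.73 | +1.10 |
| 7, 14.58 | 0.05 | +1.33 | +2.00 |
| 14, 7.58 | 0.01 | -0.35 | -0.52 |
| 14, 7.58 | 0.02 | -0.62 | -0.93 |
| 14, 7.58 | 0.05 | -1.13 | -1.69 |

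As percentages at h = 0.02, the first schedule gives 22.2% on 240 mg, 16.1% on placebo and 13.1% on 60 and 120 mg. The second gives 16.7%, 21.8% and 24.4%.

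**The case against.** The strongest reply is that the plan permits this imbalance but does not create it. The difference is proportional to F - W and is zero when they are equal. That stands. A reader might infer that 240 mg is bound to be observed for longer, or that Period 4 is open-ended. Neither is supported: the sign depends on the visit calendar, and follow-up closes Period 4.

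The size is also modest. It depends on a hazard and a gap that the documents do not give, and it sits beside an exact upper limit of 26.5% for 0/12. That stands too, though the shift is tied to dose and so is not the same thing as sampling noise. No error rate is affected, because nothing is tested.

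The time most relevant to the drug is covered equally. Subjects stay in the unit to 72 h in every period, and Protocol 3.2 places most exposure within 12 h of a dose. Escalation under Protocol 5.4 uses data to Day 4 and is untouched. Late onsets can already be picked out, because all AEs are listed (Listing 14) and time since the period's first dose is derived. But no planned summary uses that variable.

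A reader might extend the point equally to Tables 2.3-2.4. Those hold drug-related AEs only, and Protocol Appendix 4 has the investigator weigh timing and alternative causes when judging causality. Late background events are what that judgement should remove, so the concern rests mainly on Tables 2.1-2.2.

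**Conclusion.** The point holds as a qualified one. The AE windows can differ in length by dose, and the all-AE percentages in Tables 2.1-2.2 carry no allowance for it. Under the assumed hazards of 0.01-0.05 per day, and windows of about 7 to 14 days, scheduling alone shifts the 240 mg count by roughly 0.4 to 2 subjects of 12. The shift against placebo is two thirds of the shift against 60 or 120 mg. Gaps longer than 14 days would widen it; the July to September 2018 study period (Protocol 12.8.3) limits but does not exclude them. The calculation assumes 12 completers, a constant hazard and the same W for everyone.

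It is tempting to conclude that the main tables should be cut at 7 days after the first dose. The schedule does not support that. Follow-up is at least 7.58 days after the first dose, so every Period 4 exposure, including 9 of 12 to 240 mg, would lose its late scheduled check. With 7-day gaps, Periods 1-3 would keep the next period's Day -1 laboratory tests and examinations, about 6 days after dosing. One dose-linked imbalance would replace another.

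**What to change.** Keep Tables 2.1-2.4 on the full windows of SAP 9.3.1.1. Add to Tables 2.1-2.2 a by-treatment column, or one supplementary table, limited to a window with the same length and the same scheduled assessments in every period. Onset from the period's first dose through the 72 h discharge assessments is one such window, because the Schedule of Activities for Days 1-4 is common to all four periods. Put later onsets in a separate column. Show total days at risk per treatment, or events per subject-day, so that any remaining difference in window length is visible.

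This uses *Time since Period First Dose*, which the SAP already derives, plus recorded dosing and visit dates. It needs no new data and no protocol change. The cost is one extra display with sparser counts and a short note in SAP 7.1.1.
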